6.3.2 Treatment assignment, randomization

The randomization numbers will be generated using the following procedure to ensure that treatment assignment is unbiased and concealed from participants and investigator staff. A participant randomization list will be produced by the IRT system provider using a validated system that automates the random assignment of participant numbers to randomization numbers. These randomization numbers are linked to the different treatment groups, which in turn are linked to medication numbers. A separate medication list will be produced by or under the responsibility of Novartis Drug Supply Management using a validated system that automates the random assignment of medication numbers to the package containing the investigational drug(s).

At Visit 2/Baseline, all eligible participants will be randomized via Interactive Response Technology (IRT) to one of the two treatment groups in 1:1 ratio (inclisiran + usual care vs usual care). The investigator or his/her delegate will contact the IRT after confirming that the participant fulfills all the inclusion/exclusion criteria. The IRT will assign a randomization number to the participant, which will be used to link the participant to a treatment group and will specify a unique medication number for the first package of study treatment to be dispensed to the participant.

The randomization scheme for participants will be reviewed and approved by a member of the Novartis Biometrics group.

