8.4.1 Laboratory evaluations

Specimens will be obtained at the time points in the Assessment Schedule (Table 8-1).

A central laboratory will be used for analysis of all specimens collected, with the exception of urine pregnancy tests and urine dipstick tests, which will be done locally at the site (using testing materials supplied by the central laboratory). Serum pregnancy tests at screening will be done by the central laboratory. Details on the collections, shipment of samples and reporting of results by the central laboratory are provided to investigators in a Laboratory Manual.

In case of abnormal dipstick urinalysis results, microscopy and other assessments (e.g. serum albumin and serum total protein) will be performed at the local laboratory and the abnormality recorded as an AE.

Clinically significant abnormalities must be recorded as either medical history/current medical conditions or adverse events as appropriate.

Clinically notable laboratory findings are defined in Section 16.1

Local laboratory assessments may be performed on an as-needed basis for unscheduled visits. Laboratory values that exceed the boundaries of a notable laboratory abnormality must be commented on by the investigator on the source document and additional laboratory evaluations should be performed, as judged appropriate by the investigator. If the laboratory abnormality induces clinical signs or symptoms, or requires therapeutic intervention, then the diagnosis or medical condition must be entered on the patient's AE eCRF. If the laboratory abnormality is the primary reason for an unforeseen hospitalization or otherwise fulfills the seriousness category of an AE, then the procedure for rapid notification of SAEs must be followed. Likewise, if the laboratory abnormality leads to discontinuation from the study drug (temporarily or permanently), the patient must be followed until the abnormality resolves or until it is judged to be permanent. This investigation may include continued monitoring by repeat laboratory testing or by performing additional laboratory tests as deemed necessary by the investigator or the Novartis medical monitor.

As per Section 4.6, during a Public Health emergency that limits or prevents on-site study visits, if a visit by site staff/home nursing staff is arranged, specimen samples should be collected during the visit and processed and handled in line with the study laboratory manual.

Table 8-3 Clinical Laboratory Assessments

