- Dose Reduced/increased
- Drug interrupted/withdrawn
- 6. Its outcome (i.e., recovery status or whether it was fatal)

Conditions that were already present at the time of informed consent should be recorded in medical history of the participant.

Adverse events (including lab abnormalities that constitute AEs) should be described using a diagnosis whenever possible, rather than individual underlying signs and symptoms.

Adverse event monitoring should be continued for at least 30 days following the last dose of study treatment.

Once an adverse event is detected, it must be followed until its resolution or until it is judged to be permanent (e.g., continuing at the end of the study), and assessment must be made at each visit (or more frequently, if necessary) of any changes in severity, the suspected relationship to the interventions required to treat it, and the outcome.

Information about adverse drug reactions for the investigational drug can be found in the Investigator's Brochure (IB).

Abnormal laboratory values or test results constitute adverse events only if they fulfill at least one of the following criteria:

- they induce clinical signs or symptoms
- they are considered clinically significant
- they require therapy

Clinically significant abnormal laboratory values or test results must be identified through a review of values outside of reference ranges/clinically notable ranges, significant changes from baseline or the previous visit, or values which are considered to be non-typical in participants with the underlying disease. Alert ranges for laboratory abnormalities are included in Section 16.1 (Appendix 1).

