2.1.1 General definitions

Study treatment

The following are the investigational treatments:

- Inclisiran (KJX839), 284 mg, 1.5 ml liquid in a single-use prefilled syringe (PFS) for s.c. administration plus usual care
- Usual care alone

The following treatment labels will be used for all tables, listings and figures:

- Inclisiran + Usual Care
- Usual Care

Study treatment start and end date

Study treatment start date is defined as the first date when a non-zero dose of study drug is administered for the inclisiran + usual care group. If a participant, who is randomized to the inclisiran + usual care group, does not take any study drug then treatment start date will be the randomization date.

For the usual care alone group the study treatment start date will be the randomization date.

“Day 1” will be used to identify study treatment start date for both treatments.

Study treatment end date is defined as the treatment phase completion date recorded on the “Treatment Disposition” CRF for inclisiran + usual care participants. For the usual care alone group, the study treatment end date is the last recorded contact/participation date in the database.

Study start and end date

Study start date is defined as the first date when a non-zero dose of study drug is administered for the inclisiran + usual care group. If a participant, who is randomized to the inclisiran + usual care group, does not take any study drug then study start date will be the randomization date.

For the usual care alone group the study start date will be the randomization date.

Study end date is defined as the date of last recorded contact/participation date in the database.

Duration of exposure to inclisiran

For the inclisiran + usual care group, duration of exposure to inclisiran (in days) is defined as the number of days from Day 1 to the study *treatment* end date. Duration of exposure will not be defined for the usual care alone group.

Planned and actual treatment definitions

The following definitions will be used for planned and actual treatment.

Table 2-1 Planned and Actual Treatment Definitions

Randomized Treatment Group	Inclisiran Use Scenario During Study (Inclisiran Use Recorded as Study Treatment or Concomitant Medication)	Planned Treatment	Actual Treatment
Inclisiran + Usual Care	Received at least one dose of inclisiran	Inclisiran + Usual Care	Inclisiran + Usual Care
Inclisiran + Usual Care	Never received inclisiran	Inclisiran + Usual Care	Usual Care

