2.7.1 Adverse events (AEs)

The Medical Dictionary for Regulatory Activities (MedDRA) dictionary will be used for coding AEs, and up-versioning will be applied during the course of study. The final MedDRA version used in this study will be v27.0. Partially missing AE dates will be imputed following Appendix 5.1.2. An AE (classified as preferred term) occurring during the treatment period will be counted as a treatment-emergent AE (TEAE) either if it is not present at Day 1 before treatment or if it is present before treatment but increased in severity during the treatment period. Therefore, all recorded AEs with onset on or after the study treatment start date will be counted as TEAE. In case the AE date values do not allow unequivocally allocating an AE record to TEAE or non-TEAE, the AE will be considered as TEAE in the statistical analysis. The following summary tables will be presented:

- Overall Summary of TEAEs
- TEAEs by System Organ Class (SOC) and Preferred Term (PT)
- TEAEs by PT
- Common ($\geq 3\%$ within either treatment group) by PT
- TEAEs by SOC, PT, and Severity
- TEAEs by SOC, PT, and Relationship to Study Treatment
- Related TEAEs by SOC, PT, and Severity
- Treatment Emergent Serious AEs (TESAEs) by SOC and PT
- TESAEs by PT
- TESAEs by SOC, PT, and Severity
- TESAEs by SOC, PT, and Relationship to Study Treatment
- Related TESAEs by SOC, PT, and Severity
- TEAEs Leading to Withdrawal of Study Treatment by SOC and PT
- TEAEs with a Fatal Outcome by SOC and PT

If more than one event occurred with the same PT for the same participant, the participant will be counted only once for that PT using the most severe or related occurrence for the summary by severity, or relationship to study drug, respectively.

Missing severity and relationship will not be imputed and will be identified as 'missing' in the tables.

For common (3% within either treatment group) TEAEs, serious TEAEs and TEAEs leading to withdrawal of study treatment, risk ratios along with 95% confidence intervals will be presented to compare treatment groups with respect to risk.

For tables presented by SOC and PT, system organ classes are sorted alphabetically and within each system organ class, the preferred terms are sorted in descending order of total frequency.

For tables presented by PT, preferred terms are sorted in descending order of total frequency.

Listings will be presented for participants with SAEs and AEs leading to discontinuation of study treatment.

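### Protocol 8.4.1 and 10.1.1 conflict on when an abnormal urine dipstick is an AE, and SAP 2.7.1 contradicts itself on whether one found at the Visit 2 baseline test is treatment-emergent

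*Protocol*

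**What the plan says.** **Recording.** Protocol 8.4.1 says that after an abnormal dipstick, microscopy and other tests "will be performed at the local laboratory and the abnormality recorded as an AE". The next sentence is narrower: "Clinically significant abnormalities must be recorded as either medical history/current medical conditions or adverse events as appropriate". Protocol 10.1.1 sets the general rule: "Abnormal laboratory values or test results constitute adverse events only if they fulfill at least one of the following criteria". The criteria are signs or symptoms, clinical significance, or need for therapy. Section 10.1.1 also starts AE collection at informed consent and sends conditions already present at consent to medical history.

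**Timing.** Protocol Table 8-1 schedules urinalysis at Visit 2 (Day 0) and Visit 5 (Day 330) only, with none at screening. Randomization and the first inclisiran dose are also at Visit 2. SAP 2.1.1 sets the treatment start date in the inclisiran arm as the "first date when a non-zero dose of study drug is administered". For the other arm it says "For the usual care alone group the study treatment start date will be the randomization date".

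**Classification.** SAP 2.7.1 defines which AEs in the treatment period qualify as TEAEs by this test: "if it is not present at Day 1 before treatment or if it is present before treatment but increased in severity during the treatment period". The following sentence reads: "Therefore, all recorded AEs with onset on or after the study treatment start date will be counted as TEAE". AEs whose dates leave the matter unclear default to TEAE. Protocol 12.5.2 counts only events that start after the first dose, or that existed earlier and worsened.

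**The concern.** The dipstick panel in Protocol Table 8-3 has 11 items, including colour, pH and specific gravity. A trivial abnormality on any of them must be recorded under 8.4.1 and must not be under 10.1.1. Sites that read different sections will report different things, at Visit 5 as well as Visit 2.

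At Visit 2 there is a second problem. The baseline urine sample is taken on the day that the SAP calls Day 1. A pre-existing abnormality first seen in that sample, recorded as an AE and dated that day, would be a TEAE by the counting sentence and not a TEAE by the definition just before it. SAP 2.1.1 also treats a pre-dose Day 1 measurement as a baseline value, so one sample could supply both the baseline and a treatment-emergent event.

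What is at stake is the cleanness of the safety tables. Findings that study treatment cannot have caused would sit among events read as possible treatment effects.

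**Working it through.** The documents give no dipstick-abnormality rate and no expected TEAE rate, so there is no figure to reproduce. The main check is to follow one case through the text.

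**Tracing a Visit 2 finding.** Take a participant whose pre-dose Visit 2 dipstick is abnormal, with no symptoms, no therapy and no clinical significance.

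1. Under 8.4.1 it is recorded as an AE. Under 10.1.1 it is not.
2. If recorded, the natural onset date is the Visit 2 date. The dipstick is read at the site (8.4.1), and no earlier scheduled urine sample exists to date it sooner.
3. That date is the SAP start date: the randomization date in usual care and, as scheduled, the first-dose date in the inclisiran arm.
4. By the SAP definition, the finding was present on Day 1 before treatment and is not a TEAE unless it worsens. Protocol 12.5.2 agrees.
5. By the counting sentence, onset on the start date makes it a TEAE. If the date is unclear, the default is also TEAE.
6. SAP section 4, which lists departures from the protocol, does not mention the date-based rule.

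Steps 4 and 5 cannot both be programmed. In usual care there is no dose to mark what came before treatment on Day 1, so a programmer is likely to use the date rule.

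**Illustration of size, on assumed rates.** Let T be the any-TEAE rate without these records. Let b be the share of participants with an abnormal Visit 2 dipstick that is recorded as an AE and dated Day 1, independent of other events and equal in both arms. Then:

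observed rate = 1 − (1 − T)(1 − b), and participants added per arm = 192 × b × (1 − T).

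| T | b = 5% | b = 10% | b = 20% | b = 30% |
|---|---|---|---|---|
| 40% | 43.0% (+5.8) | 46.0% (+11.5) | 52.0% (+23.0) | 58.0% (+34.6) |
| 60% | 62.0% (+3.8) | 64.0% (+7.7) | 68.0% (+15.4) | 72.0% (+23.0) |
| 80% | 81.0% (+1.9) | 82.0% (+3.8) | 84.0% (+7.7) | 86.0% (+11.5) |

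The number of participants with a dipstick record is not the number added to the any-TEAE count. With b = 20%, 0.20 × 384 = 76.8 participants carry a record. At T = 60%, only 76.8 × 0.40 = 30.7 of them had no other TEAE.

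**Planned risk ratios.** SAP 2.7.1 plans these for common TEAEs (at least 3% in either arm), serious TEAEs and TEAEs leading to withdrawal of study treatment. The common threshold is 0.03 × 192 = 5.76, so six participants in one arm are enough to bring a urine-related term into that table. For one such term with assumed true rates of 3.0% and 1.5%, the true ratio is 2.00. If a share b of each arm has that same term from Visit 2:

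- b = 5%: 7.85% / 6.43% = 1.22
- b = 10%: 12.70% / 11.35% = 1.12
- b = 20%: 22.40% / 21.20% = 1.06
- b = 30%: 32.10% / 31.05% = 1.03

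The share for one term cannot exceed the share with any abnormality, so the smaller values of b are the more relevant here. Ratios for all other preferred terms are unchanged.

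**The case against.** The strongest reply is that the SAP already excludes these findings. Its definition sentence does so in terms, Protocol 12.5.2 agrees, and the baseline definition treats pre-dose Day 1 values as baseline. Read that way, Visit 2 adds no TEAEs. This stands in part. A reader might infer from the counting sentence alone that the SAP simply counts baseline dipsticks as treatment-emergent. It does not; it says both things. But the counting sentence is the one that a program can apply directly, so the conflict needs resolving.

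It can also be said that the recording conflict is softened by the next sentence of 8.4.1 and by the medical-history route in 10.1.1. That helps with conditions present at consent. It does not remove the unconditional instruction for other abnormalities.

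A reader might go further and infer that TEAE rates are inflated and that the planned risk ratios will hide a real difference. The documents do not support that. Inflation needs sites to follow 8.4.1 over 10.1.1, to date the finding on Day 1, and the counting sentence to prevail. No risk ratio is planned for any TEAE overall. An incidental dipstick result would not ordinarily be serious or lead to withdrawal, so dilution would be confined largely to urine-related terms. The test falls on the same visit in both arms, so the expected effect is about equal and favours neither.

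**Conclusion.** Wrong as written, of minor severity. Two contradictions stand on the text: 8.4.1 against 10.1.1 on what is recorded, and the SAP 2.7.1 counting sentence against its own definition and Protocol 12.5.2 on what is treatment-emergent. The timing of urinalysis makes them meet at Visit 2.

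Applied literally, they would add noise to overall TEAE incidence and to urine-related preferred terms, including any that reach the 3% common-TEAE table. The amount is unknown. The ranges above rest on assumed abnormality and TEAE rates, independence, equal shares in the two arms and Day 1 onset dates. The documents also do not fix the order of urine test and injection at Visit 2; the argument takes the sample as pre-dose. Neither primary endpoint is touched.

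**What to change.** **Protocol 8.4.1.** Replace the unconditional instruction with one that records a dipstick abnormality as an AE only if it meets the 10.1.1 criteria. Use medical history only for conditions present at consent. Sending every Visit 2 abnormality to medical history would create a new conflict. AE collection starts at consent, and a qualifying abnormality that arises between consent and Visit 2 is an AE, though not a treatment-emergent one.

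**SAP 2.7.1.** Amend the counting sentence so that AEs first identified from Visit 2 baseline assessments are non-treatment-emergent unless they worsen afterwards. This means pre-dose assessments in the inclisiran arm and the baseline visit sample in usual care. State that the rule takes precedence over the default for unclear dates. This matches the SAP's own definition and Protocol 12.5.2.

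**Cost.** Wording changes only, with no new assessment. The documents describe no field linking an AE to the sample that revealed it. The SAP should therefore say how such AEs are found, for example by checking urine-related AEs dated Day 1 against the Visit 2 urinalysis, which Table 8-1 marks as recorded in the database. If Visit 2 testing is already complete, the protocol change cannot alter those records and the SAP change does the work.

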8.4.2 Electrocardiogram (ECG)

A standard 12 lead ECG will be performed at Visit 1. Interpretation of the tracing must be made by a qualified physician and documented on the ECG section of the eCRF. Each ECG tracing should be labeled with the study, participant number and date and kept in the source documents at the study site.

Clinically significant abnormalities must be recorded on the CRF as either medical history/current medical conditions or adverse events as appropriate.

8.4.3 Pregnancy and assessments of fertility

All pre-menopausal women who are not surgically sterile will have a serum pregnancy test (hCG) performed at Visit 1 (central lab). In addition, these participants will have a urine pregnancy test conducted at the local site for Visits 2, 3, 4 and 5. If any of these tests are positive at Visits 1 and 2, the participant should not be enrolled in the trial. If a participant should become pregnant during the trial, the participant may remain in the trial for follow-up visits but cannot continue to receive inclisiran injections if randomized to the inclisiran arm.

During a Public Health emergency that limits or prevents on-site study visits, a urine home pregnancy test kit may be used. Relevant participants can perform the urine pregnancy test at home and report the result to the site. If a visit by site staff/home nursing staff is arranged, it is important that participants perform the urine pregnancy test first, and only if the test result is negative, proceed with the administration of the study treatment.

8.4.4 Other safety evaluations

Injection site reactions

Injection site reactions (ISR) should be monitored at each visit from the Randomization (Day 1) visit onwards (Table 8-1) and through additional contacts with the participant between visits as needed. ISR including individual signs or symptoms at the injection site following study treatment administration should be recorded on an appropriate eCRF page. Every effort should be made to follow-up with the participant until resolution of the ISR.

Anaphylactic reactions

Potential anaphylactic reactions should be assessed by Sampson criteria in Section 16.4 (Appendix 4).

Hyperglycemia-related events

Laboratory results and newly added concomitant medications should be checked for potential hyperglycemia-related AEs.

'New onset of diabetes' should be reported as AE on the eCRF in participants with no medical history of diabetes when:

- HbA1c becomes >6.5% and/or
- Two consecutive values of FPG are \geq 126 mg/dL (7.0 mmol/L)
- If a new concomitant medication for control of plasma glucose is added, further information to assess for a diagnosis of new onset diabetes will need to be collected

'Worsening of glycemic control' should be reported as AE on the eCRF in participants with a medical history of diabetes (HbA1c \geq 6.5% at baseline) when:

• HbA1c increases from baseline >0.5%

 New concomitant medication or increase in dose of current antidiabetic therapy is initiated to improve the control of plasma glucose level

8.4.5 Appropriateness of safety measurements

The safety assessments selected are standard for the evaluation of recent ACS patients with ASCVD and elevated LDL-C and take into consideration the safety data obtained from previous clinical studies with inclisiran.

8.5 Additional assessments

No additional tests will be performed on participants entered into this study.

8.5.1 Clinical Outcome Assessments (COAs)

Clinical Outcome Assessments refer to the assessment (investigator determination) of major adverse cardiovascular events (MACE) during the trial (incidences of cardiovascular death, non-fatal MI, resuscitated cardiac arrest, or non-fatal ischemic stroke).

[figure not shown]

[figure not shown]
8.5.3 Biomarkers

Blood samples for assessment of lipoprotein(a) (Lp(a)) will be collected at baseline and at all study visits as indicated in Table 8-1 (Assessment Schedule).

All results from Lp(a)

measurements should be blinded for participants, investigator staff, and persons per assessments. If permitted by local governing regulations and by IRB/EC, it is required as part of this protocol that the Investigator presents the following option to the participant: Additional blood samples will be collected at four time points (see Table 8-1) and biobanked to allow analysis of other biomarkers and proteins related to cardio-metabolic disease or study drug mechanism during or after study close.

9 Study discontinuation and completion

